8.2.2. Secondary Mucosal Immunogenicity Analyses

Secondary mucosal immunogenicity endpoints are as described in Section 3.2.2.2.

Summaries and analyses will be the same as secondary systemic immunogenicity endpoints with the following exceptions:

1. the pre-boost baseline is defined as the value collected on Day 78/Visit 4 prior to boost vaccination. If the visit is missed on Day 78 but the subject arrives for boost vaccination, then a sample obtained prior to the vaccination will be used as the pre-boost value.
2. All mucosal immunogenicity endpoints will be calculated and summarized based on absolute titer response over baseline and by standardizing pertussis specific ELISA responses relative to non-pertussis specific total mucosal secretion of total IgA .

8.2.3. Secondary Colonization Analyses

Secondary colonization endpoints are as described in section 3.2.2.3. Analyses on these endpoints are listed below.

- Proportion of subjects with positive *B. pertussis* by bacterial culture of nasal sample collected on each of day and on any of Days 92, 96, and 113 will be summarized based on Immunogenicity Analysis Set.
- *B. pertussis* colony counts on each day (Days 92, 96, and 113) will be summarized based on Immunogenicity Analysis Set.
- Number of subjects who remain culture positive for *B. pertussis* at Days 78 (following priming) and 254 (following boost) will be summarized based on Immunogenicity Analysis Set.

Data will be summarized for each endpoint as described in Section 4.

Listings will be provided for colonization data as collected.

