7.7.3 Analysis of Secondary Immunogenicity Endpoint

The secondary nasal **mucosal** immunogenicity endpoints will be summarized by treatment arm. Analyses will include the GMTs along with corresponding 95% CIs and GMFRs from baseline at each time point and maximum titer or ratio at any time point, as well as the proportion of subjects with seroconversion, defined as a 2-fold increase in S-IgA over baseline or 4-fold over the minimal limit of assay detection at any time point and at each time point. The baseline refers to screening and Day 78 prior to boost vaccination.

Systemic immune responses in terms of seroconversion of IgG and IgA antibody titers (PT, FHA, PRN, FIM 2/3, or BPZE1 whole cell extract for IgG only) will be summarized by treatment arm. Analyses will include the GMTs along with corresponding 95% CIs and GMFR at each time point and maximum titer or ratio at any time point, as well as the proportion and 95% CI of subjects achieving seroconversion (defined as 2-fold increase over baseline or 4-fold increase over the minimum limit of detection) at any time point and at each time point.

Colonization data will be summarized by treatment arm at available time points. Analysis will include dichotomized results (Yes/No) for *B. pertussis* culture along with colony counts from Days 92 to 113 following vaccination with BPZE1 or placebo. The effect of recent and post vaccination with BPZE1 on absolute colony counts and clearance of colonization will be assessed for this period. The analyses will include proportion of subjects with positive *B. pertussis* at Day 78 (prior to boosting vaccination) as well as Day 254 (end-of-study).

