4.3.2. Immunogenicity Analysis Set

The Immunogenicity Analysis Set will include all the Intent to Treat subjects who received the prime dose of the study vaccine(s) and have contributed both pre- and at least 1 post prime vaccination sample (mucosal or serum immunogenicity testing, respectively) for which valid results were reported and who have not received any component of a licensed pertussis vaccine in the 5 years through Day 113 of the study. Subjects will be classified according to the study vaccine received. For analysis of boosting, those subjects who have received all vaccinations and have a pre (Day 78 for mucosal and Day 85 for serum) and a post boost immune sample (Day 113) for which valid results were reported will be utilized. Additional testing for maximum response will be assessed for those subjects who received all vaccinations and have both a baseline sample (screening or Day 1 depending on the sample type) and a sample at Day 113. Immune persistence will be assessed in those subjects who contribute to sampling at Days 169 and 254.

Subjects will be classified according to the study vaccine received and according to humoral and mucosal immunity samples as described. Subjects who discontinued from study will be classified according to randomized treatment arm. Subjects who missed a boost dose, will be classified to no boost treatment arm based on prime arm. Subjects who received wrong vaccination by mistake and discontinued from study will be classified according to actual vaccination, priority higher.

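### Colonization and carriage tables use an analysis set defined by antibody results, so a vaccinated, cultured subject without a valid antibody baseline drops out of them

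*SAP*

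**What the plan says.** SAP 8.2.3 names the same set for each colonization endpoint:

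- Culture positivity, by day and overall: "on any of Days 92, 96, and 113 will be summarized based on Immunogenicity Analysis Set".
- Colony counts: "colony counts on each day (Days 92, 96, and 113) will be summarized based on Immunogenicity Analysis Set".
- Persistent positivity: "at Days 78 (following priming) and 254 (following boost) will be summarized based on Immunogenicity Analysis Set".

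SAP 4.3.2 (and Protocol 7.5, in the same terms) admits subjects who received the prime dose and "have contributed both pre- and at least 1 post prime vaccination sample (mucosal or serum immunogenicity testing, respectively) for which valid results were reported". It also limits the set to those "who have not received any component of a licensed pertussis vaccine in the 5 years through Day 113 of the study", which I take to mean a non-study vaccine, since Boostrix is a study product. For analyses of boosting it asks for all vaccinations and that subjects "have a pre (Day 78 for mucosal and Day 85 for serum) and a post boost immune sample (Day 113") with valid results. Culture plays no part in any of these rules.

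SAP 4.6 does not impute missing immunogenicity data. SAP 8.3 plans a sensitivity analysis for the primary endpoint only, on the Per Protocol set, which is a subset of the same set. SAP 8.2.3 ends by promising listings of the colonization data as collected. Protocol 7.7.3 says: "Colonization data will be summarized by treatment arm at available time points".

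**The concern.** A culture result is interpretable if the subject was vaccinated and a valid swab was cultured. It has no antibody baseline and needs none. The chosen set nevertheless makes a subject's place in the colonization tables depend on antibody samples, and because culture is neither mucosal nor serum antibody testing, the SAP does not say which version of the set applies.

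Two results are affected. The Day 92 to 113 cultures address the stated hypothesis that BPZE1 priming, unlike Boostrix priming, reduces colonization after a BPZE1 boost (Protocol 1.2, SAP 1). That contrast rests on arm A against arm C, and arm C has only 50 planned subjects. The Day 78 and Day 254 counts are the tabulated record of persistent carriage of a live strain. Protocol 3.1 does not expect chronic carriage, so the count should be near zero and a single subject matters.

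**Working it through.** **Inputs.** Planned arm sizes are A 100, B 100, C 50 and D 50 (SAP Table 3-1). The 10^7 CFU lead-in has 16 BPZE1-primed and 8 Boostrix-primed subjects, half of each boosted with BPZE1 at 10^7 (SAP Table 3-2 and section 3.1). Intervals are two-sided 95% Clopper-Pearson (SAP 4). The documents give no sample-failure rate, so q, the chance that any one antibody sample is missing or invalid, is assumed at 2%, 5% and 10%, independently across samples.

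**The plan's own figure.** For 80% response at N = 50, exact limits are 66.3% to 90.0%, width 23.7, as in SAP Table 4-1. All 20 cells of that table reproduce to 0.1 point.

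**Relevant denominators.**
- Primed at 10^9: 200 − 16 = 184.
- Boosted with BPZE1 at 10^9: A 100 − 8 = 92, C 50 − 4 = 46, total 138.

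**Who is lost under the set as named.** A subject fails if the baseline is missing, or if every post-prime sample is. Counting only the two post-prime samples before the boost:

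P(excluded) = q + (1 − q)q²

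| q | P(excluded) | Share due to baseline | Lost of 138 (138 × q) |
|---|---|---|---|
| 2% | 2.04% | 2.0% | 2.8 |
| 5% | 5.24% | 5.0% | 6.9 |
| 10% | 10.9% | 10.0% | 13.8 |

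Later samples shrink the second term further, so the loss is almost wholly the baseline. If a valid pair of either sample type were enough, both types would have to fail. The loss would then be about q²: 0.04%, 0.25% and 1%.

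**Effect on a rate.** Take N = 50 and 80% positive (Protocol 1.1 reports more than 80% in Phase 1b), that is 40/50. Losing 10% at random gives 36/45 = 80.0% (65.4% to 90.4%), width 25.0 instead of 23.7. The arithmetic extremes are 35/45 = 77.8% if all five lost are positive and 40/45 = 88.9% if all five are negative.

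**Effect on a carriage count.** Suppose all 184 are cultured on Day 78 and one is positive: 1/184 = 0.5%, CI 0.01% to 3.0%. If that subject has no valid antibody baseline, the table shows 0/183, CI 0% to 2.0%.

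**If the boosting clause were applied to Days 92 to 113.** Baseline, pre-boost and Day 113 results would all be needed:

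P(excluded) = 1 − (1 − q)³ = 5.9%, 14.3% and 27.1%

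Days 92 and 96 have cultures but no antibody sampling, so inclusion there would depend on a visit 113 − 96 = 17 to 113 − 92 = 21 days later. With an assumed 15% of colonized and 5% of other subjects missing Day 113, a true 70% would be shown as

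0.70 × 0.85 / (0.70 × 0.85 + 0.30 × 0.95) = 0.595 / 0.880 = 67.6%

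**The case against.** The strongest reply is that little is lost and nothing is biased. One missing post-prime sample excludes nobody if another is valid, and a subject cultured on Days 92 to 113 has normally passed several. The baselines (nasal at screening, serum on Day 1) precede vaccination, so later colonization cannot cause their absence. Day 78 and Day 113 cultures share a visit with nasal antibody sampling, so some losses would coincide anyway. The study is descriptive and tests no hypothesis. All of this stands, and it limits the point to lost subjects and the occasional lost carrier.

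Three stronger readings are tempting, and the documents do not support them:

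- **That Day 92 and 96 results are conditioned on a Day 113 antibody sample and so biased.** SAP 8.2.3 does not invoke the boosting clause, whose paired samples fit the antibody fold-rise endpoints. The SAP leaves its scope unclear, which calls for clarification. Even then, the 2.4-point shift above (70% to 67.6%) is small beside the plan's interval widths at 70%: 26.7 points at N = 50 and 18.7 at N = 100.
- **That the SAP departs from the protocol without declaring it in SAP 11.** The phrase about available time points in Protocol 7.7.3 concerns visits, not populations. It sits in a secondary immunogenicity section, and Protocol 7.7.1 presents immunogenicity data on this set.
- **That a positive culture disappears from the record.** It leaves the summary tables. The colonization listing is of data as collected and is not limited to this set, unlike the antibody listings in SAP 8.1 and 8.2.1.

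A further fair point is that abandoning the set also abandons its criterion on other pertussis vaccines, which is relevant to a colonization comparison. The fix retains it in the sensitivity analysis.

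None of this gives a reason to make a culture result depend on an antibody result.

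**Conclusion.** The concern holds in a limited form. Following SAP 8.2.3 and 4.3.2 as written removes vaccinated, validly cultured subjects from every colonization and carriage table when the antibody baseline is missing or invalid, and no other set or sensitivity analysis covers these endpoints.

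The usual effect is a modest loss of precision: about 3 to 14 of 138 subjects at assumed failure rates of 2% to 10%, and fewer if either sample type qualifies. The effect that could change a reading is on rare carriage, where a tabulated 1/184 can become 0/183 and only the listing would show the case. That example assumes full Day 78 culture and a carrier who happens to lack the baseline. Selection bias is not established. It would need the boosting clause to apply and missingness to differ by colonization status, and the documents state neither.

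**What to change.** In SAP 8.2.3:

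1. Summarize Days 92, 96 and 113 in all subjects who received the Day 85 dose and have a valid culture at that visit, by vaccine received and regardless of antibody samples.
2. Report Day 78 and Day 254 positives on the Safety Analysis Set, with the number cultured beside each count. This matters most at Day 254, where only subjects positive on Day 113 are cultured.
3. Keep the Immunogenicity Analysis Set version as a sensitivity analysis, which also retains its criterion on non-study pertussis vaccine. State which sample type defines membership there and whether the boosting clause applies.

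The cost is SAP wording and one extra set of tables, with no new data or visits. The downside is that colonization and antibody tables will have slightly different denominators, which a footnote can explain.

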8.3. Sensitivity and Subgroup Analyses

Sensitivity analysis for primary endpoint will be performed based on the Per Protocol Analysis Set.

Subgroup analysis will be performed for following mucosal and systemic endpoints by positive baseline status (yes/no) of pertussis antibodies against PT, PRN, FHA, FIM 2/3, BPZE1 whole cell extract, and at least one antigen (PT, or FHA, or PRN).

- Proportion of subjects achieving seroconversion on Day 29 or 113.

In addition, subgroup analysis will be performed for following mucosal and systemic endpoints by positive baseline status (yes/no) of pertussis antibodies against PT, PRN, FHA, FIM 2/3, and BPZE1 whole cell extract.

- The Geometric Mean Fold rise (GMFR) against each pertussis antigen (PT, FHA, PRN, FIM 2/3, and BPZE1 whole cell extract):
- The Geometric Mean Titer (GMT) against each pertussis antigen (PT, FHA, PRN, FIM 2/3, and BPZE1 whole cell extract)

8.4. Exploratory Analysis

- The GMT expressed for serum IgG ELISA against tetanus and diphtheria on Days 29 and 113.

The GMT will be summarized using descriptive statistics (mean, median, standard deviation, min, max) along with 95% CI, by each pertussis antigen on Days 29 and 113 based on Immunogenicity Analysis Set.

- T-cell responsiveness utilizing PBMC stimulated cells. Responsiveness (day 8 and 92) will be analyzed relative to baseline as well as absolute value.

The exploratory analyses will be completed in the future with subject treatment assignment maintaining the blind for the laboratory personnel conducting the testing.

9. Safety Analysis

Unless otherwise specified, safety analysis will be performed based on the Safety Analysis Set. All summaries and analyses will be presented over all subjects and by treatment arms for the prime (Day 1 vaccination) and boost (Day 85 vaccination) periods. Summaries of the prime period will be presented based on treatment arms of BPZE1 prime (A, B, A+B), Boostrix prime (C, D, C+D) and Total (A+B+C+D). Summaries of the boost period will be presented based on treatment arms of BPZE1 prime with BPZE1 boost (A), BPZE1 prime with no boost (B), Boostrix prime with BPZE1 boost (C) and Boostrix prime with no boost (D), Total Post Booster BPZE1 (A+C), and Total Post Placebo Boost (B+D), Total Any BPZE1 Exposure (A+B+C) and Total (A+B+C+D).

9.1. Solicited Adverse Events

One of the primary safety endpoints of the study are solicited adverse events (local, nasal/respiratory, and systemic reactogenicity events) for 7 days following vaccination by severity score, duration, and peak intensity. Local reactogenicity are only collected after Day 1 vaccination, while nasal/respiratory and systemic reactogenicity are collected after both Day 1 and Day 85 vaccination. Solicited adverse events (AEs) are collected at 60 minutes (\pm 15 minutes) after each vaccination at the site (in-clinic assessment). In addition, subjects will record reactogenicity in the daily subject diary starting post-vaccination for 7 additional days (after each vaccination). For each vaccination, specific local (arm), nasal/respiratory, and general systemic reactogenicity reactions will be graded by the investigator using standard toxicology grading at the subsequent visit following vaccination (see Table 9-1).

Solicited reactogenicity adverse events (AEs) will be summarized for local reactogenicity, nasal/respiratory reactogenicity, and systemic reactogenicity adverse events separately based on the Safety Analysis Set and relative to the most recent vaccination given. For prime vaccination the results of greatest interest are A+B (Total Post BPZE1 prime) and C+D (Total Post Boostrix prime). For the boost vaccination the results of greatest interest are A+C (Total Post Booster BPZE1) and B+D (Total Post Placebo boost). In the case of the Safety Lead-in Analysis set subjects assigned to 10^7 and 10^9 BPZE1 will be tabulated separately.

Frequency counts will be provided by severity grades for each symptom (Table 9-1) for the following:

- On the day of vaccination (Day 1 and Day 85) within 60 mins (\pm 15 minutes) after each vaccination at the site (in-clinic assessment)
- Highest score in each past 24 hours (with the first score recorded on Day 1 post vaccination) through Day 7.
- Maximum severity grade over 7 days.

Additionally, maximum severity will be dichotomized into a binary variable (mild, moderate or severe vs none) and to be summarized as proportion with 2-sided 95% CI using Clopper Pearson methods. Grade 0 (none) will be the classification if the observation is less than a Grade 1.

Fever – oral, Erythema/redness, and Induration/swelling for 7 days following each vaccination will be summarized using descriptive statistics (mean, standard deviation, median, min, max).

Duration through 7 days and Duration through resolution will be summarized using descriptive statistics (mean, standard deviation, median, min, max). Duration through 7 days is defined as days with the reactogenicity event onset through 7 days following vaccination per patient reported daily diary. Duration beyond 7 days is defined as days with the reactogenicity event continuing beyond 7 days as captured in adverse events. Duration Through Resolution is defined as days with the reactogenicity event onset until resolution, which includes duration through 7 days and duration beyond 7 days. Duration beyond 7 days will be listed in adverse event listing.

Listings will be provided for each type of reactogenicity based on the Safety Analysis Set.

Table 9-1

Local Reactogenicity Grading

Local Reaction to Injectable Product	Mild (Grade 1)	Moderate (Grade 2)	Severe (Grade 3)	Potentially Life Threatening (Grade 4)
Pain	Does not interfere with activity	Repeated use of nonnarcotic pain reliever >24 hours or interferes with activity	Any use of narcotic pain reliever or prevents daily activity	Emergency room visit or hospitalization
Tenderness	Mild discomfort to touch	Discomfort with movement	Significant discomfort at rest	Emergency room visit or hospitalization
Erythema/redness ^a	2.5 to 5 cm	5.1 to 10 cm	>10 cm	Necrosis or exfoliative dermatitis
Induration/swelling ^b	2.5 to 5 cm and does not interfere with activity	5.1 to 10 cm or interferes with activity	>10 cm or prevents daily activity	Necrosis

Nasal/Respiratory Reactogenicity Grading				
Local Reaction	Mild (Grade 1)	Moderate (Grade 2)	Severe (Grade 3)	
Runny nose	Noticeable but does not interfere with daily activity	Moderate discomfort that interferes with daily activity	Significant discomfort/prevents daily activity or seeks medical care	
Stuffy nose/congestion	Noticeable but does not interfere with daily activity	Moderate discomfort that interferes with breathing from nose	Unable to breathe through nose or seeks medical care	
Nasal pain/irritation	Noticeable but does not interfere with daily activity	Moderate discomfort that interferes with daily activity	Significant discomfort that prevents daily activity or seeks medical care	
Epistaxis	Total duration of all episodes in a 24-hour period <30 minutes	Total duration of all episodes in a 24-hour period >30 minutes	Any bleeding that required visit for medical encounter	
Sneezing	Noticeable but does not interfere with daily activity	Moderate discomfort that interferes with daily activity	Significant discomfort; prevents daily activity	
Sinus pressure/pain	Noticeable but does not interfere with daily activity	Moderate discomfort that interferes with daily activity	Significant discomfort that prevents daily activity or seeks medical care	
Sore/irritated throat	Noticeable but does not interfere with eating or drinking	Moderate discomfort that interferes with eating or drinking	Significant discomfort that prevents eating or drinking or seeks medical care	
Cough	Noticeable but does not interfere with daily activity or sleeping	Frequent cough that interferes with daily activity or sleeping	Prevents daily activity, prevents sleep, or seeks medical care	
Shortness of breath/wheezing	Noticeable but does not interfere with daily activity	Moderate discomfort that interferes with daily activity	Significant discomfort/ prevents daily activity or seeks medical encounter	

Subjective Systemic Reactogenicity Grading			
Systemic (Subjective)	Mild (Grade 1)	Moderate (Grade 2)	Severe (Grade 3)
Fever ^c - oral ^d	100.4°F – 101.1°F	101.2°F – 102.0°F	>102.0°F
Fatigue (tiredness)	No interference with daily activity	Some interference with daily activity	Significant interference, prevents daily activity
Malaise (general unwell feeling)	No interference with daily activity	Some interference with daily activity	Significant interference, prevents daily activity
Myalgia (body aches/muscular pain)	No interference with daily activity	Some interference with daily activity	Significant interference, prevents daily activity
Arthralgia (joint pain)	No interference with daily activity	Some interference with daily activity	Significant interference, prevents daily activity
Headache	No interference with daily activity	Some interference with daily activity	Significant interference, prevents daily activity
Rash/hypersensitivity ^e	Pruritus OR local rash	Diffuse rash	Diffuse rash with blisters or mouth ulcerations, anaphylaxis, or angioedema

Note: Grade 0 will be the classification if the observation is less than a Grade 1.

- ^a In addition to grading the measured local reaction at the greatest single diameter, the measurement should be recorded as a continuous variable.
- ^b Induration/swelling should be evaluated and graded using the functional scale as well as the actual measurement.
- ^c A fever can be considered not related to the study product if an alternative etiology can be documented.
- ^d Subjects must not eat or drink anything hot or cold within 10 minutes prior to taking oral temperature. Oral temperature assessed on Day 1 prior to the first study vaccination will be considered as baseline.
- ^e Adapted from the Division of AIDS Table for Grading the Severity of Adult and Pediatric Adverse Events Version 2. 2014.

Source: DHHS 2007

9.2. Unsolicited Adverse Events

Unsolicited Adverse events will be coded according to Medical Dictionary for Regulatory Activities (MedDRA) version 22.0 or above. Unless otherwise specified, unsolicited AEs will be summarized by System Organ Class (SOC) and Preferred Term (PT), with SOCs sorted in the alphabetical order and PTs within each SOC in descending order of subject incidence. Partial missing unsolicited adverse event start dates will be imputed based on Appendix 13.4.

TEAE is defined as an AE that starts or an existing AE that worsens on or after the date of prime vaccination. AE will be summarized by period, including Day 1 to Day 84, Day 85 to Day 113, and Day 114 to End of Study (EOS). From Day 1 to Day 29, all AE regardless causality will be recorded and summarized. From Day 30 to Day 84, all AE related to vaccination and SAE will be recorded and summarized. From Day 85 to Day 113, all AE regardless causality will be recorded and summarized. From Day 114 through end of study (EOS), all SAE will be recorded and summarized.

